## 6.2. Secondary Endpoints

All efficacy endpoints are secondary and listed in [Section 3.2](#). [Table 2](#) summarizes the analysis sets to be used in the analysis of each efficacy endpoint.

The secondary efficacy endpoints will be summarized using descriptive statistics by visit for the binary and continuous endpoints respectively. The percent (for the binary endpoints) and mean change (for the continuous endpoints) over time and associated standard errors will be plotted for analyses in sJIA1, sJIA2 and pJIA analysis sets (see [Table 2](#)).

The binary endpoints are JIA ACR responses, occurrence of JIA ACR disease flare, JIA ACR clinical inactive disease status and clinical remission, occurrence of JADAS minimum disease activity and inactive disease, eligibility of tapering, partial tapering success and complete tapering success for corticosteroids, MTX/leflunomide, and tofacitinib, absence of fever for sJIA subjects at each visit. Number, frequency, percent and the associated standard error will be presented for binary variables. JIA ACR disease flare will only be summarized for those who have reached Month 3 Visit of this extension study.

The continuous endpoints are change from baseline in physician global evaluation of disease activity, number of joints with active arthritis, number of joints with limitation of motion, CRP, ESR, CHAQ, JADAS-27 CRP, JADAS-27 ESR at each visit. Number, mean, standard deviation, standard error of the mean, median, quartiles, minimum, and maximum will be presented for continuous variables.

For ERA subjects, change from baseline in TEA, Modified Schober's Test, Overall Back Pain, Nocturnal Back Pain at each visit will be summarized as continuous variables.

For PsA subjects, change from baseline in BSA affected by psoriasis, PGA of psoriasis at each visit will be summarized as continuous variables.

For ESR and any efficacy endpoint summaries involving ESR, all ESR data points including those collected with expired/non-standard ESR kits will be used for analysis. Supportive analyses will be performed to evaluate the impact of expired/non-standard ESR kits (see Section 6.2.1).

For CHAQ and any efficacy endpoint summaries (i.e., JIA ACR responses, JIA ACR flare, and JADAS) involving CHAQ, subjects with invalid CHAQ measurements will be excluded for the visits where these invalid measurements were made. Examples of invalid CHAQ measurements include:

- incorrectly translated CHAQ data
- CHAQ data collected remotely over the phone
- CHAQ completed by the subject instead of the parent/legal guardian

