An interim analysis (data cutoff 04 Jun 2019, data snapshot 03 Jul 2019) was conducted for Study A3921145. At the time of the data cutoff, 227 subjects had enrolled in the study (signed informed consent), and 2 subjects from Study A3921104 were enrolled but not treated; 177 subjects were ongoing. Insufficient clinical response was the most common discontinuation reason to date. In general, available efficacy data of long-term treatment with tofacitinib showed stable improvement in JIA symptoms from baseline of the qualifying/index studies.

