9.1. Sample Size Determination

Sample size will be determined by the number of subjects who enroll from the qualifying/index studies. Feedback from literature and Investigators indicates about 90% of subjects from qualifying/index studies would enter into this study. Therefore, approximately 340 subjects are expected to join from currently planned studies (ie, A3921103, A3921104 and A3921165). Enrollment will depend on the timing of the initiation of on-going and planned studies. Analyses performed, including interim analyses, if any, will primarily be for safety though some measures of efficacy may be analyzed, and no adjustment of sample size due to interim analyses is needed (No hypothesis testing is planned in this study).

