## **5. GENERAL METHODOLOGY AND CONVENTIONS**

### **5.1. Hypotheses and Decision Rules**

There are no hypotheses since this study is an open--label single--arm long-term follow--up study with the primary and secondary objectives achieved through descriptive statistics.

Decision rules are not applicable since there are no formal hypotheses.

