## 5.2. General Methods

In general, descriptive statistics will include number of subjects evaluated, number and percent for binary variables, and mean, standard deviation, minimum, 1st, 2nd (median) and 3rd quartiles and maximum for continuous variables. Graphics will be generated if needed.

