**Table 2. Analysis Sets for Each Efficacy Endpoint**

	sJIA1*	sJIA2*	pJIA*	ERA	PsA
--	---------------	---------------	--------------	------------	------------

\* Plots will be provided for analyses in these analysis sets, except for endpoints related to tapering.

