- Components: cardiovascular death, non-fatal myocardial infarction, and non-fatal stroke.
- Including SMQs: Hepatic failure, fibrosis, and cirrhosis, and other liver damage-related conditions; and Hepatitis, non-infectious.
- Including Acute renal failure SMQ.
- Adjudicated by an internal review committee.

Incidence Rates (IRs) will be calculated and presented in 100 subject-years and defined as follows:

$$\text{IR} = 100 * \frac{\text{Number of Unique Subjects with Event during the Risk Period (RP)}}{\text{Sum of Event Exposures for all Subjects (Subject-Years of Exposure)}}$$

The numerator of the IR will include subjects counted only once as soon as they experience a first event during their individual risk period (RP) defined below.

The denominator will be the sum of the times to event for those who experience an event during the risk period and the lengths of risk periods for those who do not experience an event. If a subject experiences multiple instances of the same event, the time to first occurrence of the event will be considered.

In general, a subject is considered at risk to experience an AE while on tofacitinib treatment and within 28 days of stopping tofacitinib treatment. Thus, the risk period extends from the subject's first dose of tofacitinib up to the date of last dose of tofacitinib + 28 days.

For the final analysis, the RP is defined as:

$$\text{RP} = \min(\text{last dose date} + 28 \text{ days}, \text{last contact date}) - \text{first dose date} + 1 \text{ day}.$$

The last contact date will be the maximum of (AE start date, AE stop date, last study visit date, withdrawal date). If a subject is dead, the last contact date will be the death date.

For an interim analysis with a data cutoff date, the RP is defined as:

$$\text{RP} = \min(\text{last dose date} + 28 \text{ days}, \text{last contact date}, \text{data cutoff date}) - \text{first dose date} + 1 \text{ day}.$$

95% CI (corresponding to  $\alpha=0.05$ ) for this IR will be calculated based on the assumption that the actual count of cases (i.e., unique subjects with events) arises from an exact Poisson distribution. The approach used in Daly (1992) describing the calculation of exact confidence limits will be used. If  $x$  denotes the actual number of subjects with events, the (1

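### Binary efficacy endpoints get only a standard error, which is zero at 0% or 100% whatever the sample size, and no confidence interval is planned

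*SAP*

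**What the plan says.** SAP 6.2 sets the display for JIA ACR response, flare, clinical inactive disease and remission, the JADAS categories, tapering and absence of fever: "Number, frequency, percent and the associated standard error will be presented for binary variables". The percent is also shown graphically, "over time and associated standard errors will be plotted for analyses in sJIA1, sJIA2 and pJIA analysis sets". The footnote to SAP Table 2 narrows this: "Plots will be provided for analyses in these analysis sets, except for endpoints related to tapering". ERA and PsA carry no plot marker in that table, so their results are tabulated only.

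SAP 5.2 (General Methods) adds only the number evaluated and "number and percent for binary variables". Neither document gives a formula for the standard error of a percentage, or an interval for any binary efficacy endpoint. The one interval method the SAP specifies is in 6.6, for safety incidence rates. There the count of subjects with events "arises from an exact Poisson distribution", exact limits follow, and the zero-count case is written out separately.

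**The concern.** The secondary objective is persistence of efficacy, and it is to be met by description alone. With no test, the displayed precision is the plan's only statement of how firm a percentage is. A standard error that vanishes at 0% or 100% shows a 10/10 cell as if it were known without error, and shows it exactly as it shows 200/200.

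Thin cells are plausible. SAP 4.4 splits the study into five overlapping sets, SAP 5.3 analyses available data only, participation length varies (SAP 2.2), and the visit windows in SAP Appendix 1.12 run to Month 120. A plotted curve that ends in points without bars could be read as strong evidence that response lasts. SAP 7 allows interim results to be used for publications, where a figure may appear without its table.

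**Working it through.** **Inputs.** Precision measure: standard error of the percent (SAP 6.2). Total size: "approximately 340 subjects are expected to join from currently planned studies" (Protocol 9.1). Interim enrolment, all subtypes together: "At the time of the data cutoff, 227 subjects had enrolled in the study" (Protocol 2.3.2). Sizes of sJIA1, sJIA2, pJIA, ERA and PsA, sizes by visit, and response rates: not given. The documents contain no standard error or interval to reproduce, so n and the true rate are varied over a range.

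**Step 1: the standard error at the boundary.** Assumed formula: SE = sqrt(p(1−p)/n). At p = 1 or p = 0 the product p(1−p) is 0, so SE = 0 for any n. Using n−1 as the divisor gives the same result.

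**Step 2: what an interval would show.** For n responders out of n, the Clopper-Pearson 95% lower limit is 0.025^(1/n) and the upper limit is 100%. For example, 0.025^(1/10) = 0.692 and 0.025^(1/20) = 0.832. The case of no responders is the mirror image: 0/10 gives 0 to 1 − 0.692 = 30.8%.

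**Step 3: how often a cell is all-or-none.** The chance is π^n + (1−π)^n for true rate π.

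| n | Planned SE at n/n | Exact 95% | Wilson 95% | Chance of all-or-none, π = 90% | Chance, π = 95% |
|---|---|---|---|---|---|
| 5 | 0 | 47.8–100% | 56.6–100% | 0.591 | 0.774 |
| 10 | 0 | 69.2–100% | 72.2–100% | 0.349 | 0.599 |
| 20 | 0 | 83.2–100% | 83.9–100% | 0.122 | 0.358 |
| 30 | 0 | 88.4–100% | 88.6–100% | 0.042 | 0.215 |
| 50 | 0 | 92.9–100% | 92.9–100% | 0.005 | 0.077 |

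At a true rate of 80% the chance is 0.107 at n = 10 and 0.012 at n = 20. At 50% it is 0.002 at n = 10. The problem therefore needs both a small cell and a rate near 0% or 100%.

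**Step 4: can a plotted bar leave the 0–100% range?** p + SE > 1 requires sqrt(p(1−p)/n) > 1−p, that is p/(1−p) > n. The largest attainable value below 100% is x = n−1, where p/(1−p) = n−1, which is less than n. So a bar of one standard error never passes 100% and, by symmetry, never falls below 0%. Checking every count for n = 2 to 340, with divisor n or n−1, gave no violation. At 19/20, SE = sqrt(0.95 × 0.05/20) = 4.87 points, and the bar runs from 90.1% to 99.87%.

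**The case against.** The strongest reply is that this is a presentational choice. The study tests nothing: "Decision rules are not applicable since there are no formal hypotheses". Efficacy is secondary, no action depends on the standard error, and the same section gives standard errors for continuous endpoints. The tables carry the number and frequency beside the percent, so a reader sees 10 of 10 and can work out an exact interval. Exact limits in SAP 6.6 serve the primary safety objective, so using a different measure for efficacy is not a contradiction. All of this stands, and it lowers the importance. It does not restore the missing bar on a plot, and it leaves the plan's only precision measure uninformative in those cells.

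Three stronger readings are tempting but unsupported.

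- A reader might infer that the bars will pass 100% near the boundary. Step 4 shows that a bar of one standard error cannot. Overshoot appears only if a reader multiplies by 1.96 (19/20 then reaches 104.6%), and the SAP plans no such interval.
- A reader might infer misleading plots for every subtype and endpoint. ERA and PsA are not plotted, and tapering is not plotted in any set.
- A reader might take it as known that these endpoints sit near 0% or 100%. Absence of fever could plausibly do so in sJIA1, which includes sJIA subjects from A3921104 whom SAP 4.4 describes as lacking active systemic features. The documents nevertheless report no rate for any of these endpoints.

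**Conclusion.** The point holds in a limited form. Binary efficacy endpoints have a standard error as their only precision measure and no interval. Under the usual formula that measure is zero in every all-or-none cell. The understatement is large where n is small (lower limit 69% at 10/10, 83% at 20/20) and slight where n is large (98% at 200/200).

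This rests on two assumptions: that the unnamed formula is the usual one, and that some visit-by-subtype cells are both small and near the boundary. The first is very likely. The second is plausible from the design, but its frequency cannot be stated because neither sizes nor rates are given. The severity is modest: the endpoints are secondary and descriptive, and the tables show counts. The change is still worth making, because it is cheap and the SAP already specifies exact limits elsewhere.

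**What to change.** In SAP 6.2, replace the standard error for binary endpoints with a two-sided 95% Clopper-Pearson interval (Wilson is also acceptable, but name one). Use it in the tables for all five sets and as the error bars in the sJIA1, sJIA2 and pJIA plots. Show n at each visit under each plot, and state in the legend that the bars are 95% limits, since the continuous plots would still show standard errors.

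The cost is about one sentence and a standard procedure option, with no new data. The visible price is width, because a 95% interval replaces a one-standard-error bar. At 19/20 the bar goes from about 90–99.9% to 75–99.9%, roughly 24.8 points against 9.7, or about 2.5 times as wide. At 10/10 it goes from nothing to 30.8 points.

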**Table 2. Analysis Sets for Each Efficacy Endpoint**

		sJIA1*	sJIA2*	pJIA*	ERA	PsA
Efficacy endpoints defined for all subjects						
	Change from baseline (CFB) in CRP and ESR	Y	Y	Y	Y	Y
	CFB in physician global evaluation of disease activity	Y	Y	Y	Y	Y
Joint assessment	CFB in number of joints with active arthritis	Y	Y	Y	Y	Y
	CFB in number of joints with limitation of motion	Y	Y	Y	Y	Y
CHAQ	CFB in CHAQ Disability Index	Y	Y	Y	Y	Y
	CFB in CHAQ Discomfort Index	Y	Y	Y	Y	Y
	CFB in CHAQ Parent's Global Assessment of Overall Wellbeing	Y	Y	Y	Y	Y
JIA ACR	JIA ACR 30/50/70/90/100 response	Y	Y	Y	Y	Y
	JIA ACR disease flare after Month 3	Y	Y	Y	Y	Y
	JIA ACR Clinical Inactive Disease	Y	Y	Y	Y	Y
	JIA ACR Clinical Remission	Y	Y	Y	Y	Y
JADAS-27 CRP & JADAS-27 ESR	Change from baseline	Y	Y	Y	Y	Y
	JADAS minimum disease activity	Y	Y	Y	Y	Y
	JADAS inactive disease	Y	Y	Y	Y	Y
Tapering for corticosteroids, MTX/leflunomide and tofacitinib, respectively	Achieving eligibility of tapering	Y	Y	Y	Y	Y
	Achieving partial tapering success	Y	Y	Y	Y	Y
	Achieving complete tapering success	Y	Y	Y	Y	Y
Efficacy endpoints defined for specific subtypes						
In subjects with sJIA	Achieving "Absence of Fever"	Y	Y	NA	NA	NA
In subjects with ERA	CFB in TEA	NA	NA	NA	Y	NA
	CFB in Modified Schober's Test	NA	NA	NA	Y	NA
	CFB in Overall Back Pain	NA	NA	NA	Y	NA
	CFB in Nocturnal Back Pain	NA	NA	NA	Y	NA
In subjects with PsA	CFB in BSA affected by psoriasis	NA	NA	NA	NA	Y
	CFB in PGA of psoriasis	NA	NA	NA	NA	Y

**Table 2. Analysis Sets for Each Efficacy Endpoint**

	sJIA1*	sJIA2*	pJIA*	ERA	PsA
--	---------------	---------------	--------------	------------	------------

\* Plots will be provided for analyses in these analysis sets, except for endpoints related to tapering.

### 6.2.1. Supportive Analyses

Supportive analyses will be performed in order to evaluate the impact of expired/non-standard ESR kits. For endpoints that take ESR as one of the components, ESR data collected with expired/non-standard ESR kits will be excluded (i.e., considered missing) and descriptive statistics will be provided by visit based on available data. Supportive analyses will be done in sJIA1, sJIA2, pJIA, ERA and PsA, separately.

- The following endpoints will be considered missing after excluding ESR data, which includes:
  - change from baseline in ESR
  - change from baseline in JADAS-27 ESR score
  - occurrence of JADAS minimum disease activity and inactive disease calculated from JADAS-27 ESR score
  - JIA ACR clinical inactive disease status and clinical remission
- For JIA ACR responses and occurrence of JIA ACR disease flare, the response status will be determined using the available components after excluding ESR data.

The list of ESR data points to be excluded will be determined before data base release.

### 6.3. Exploratory Endpoints

Plasma concentration -time data for tofacitinib will be analyzed using a nonlinear mixed effects modeling approach to characterize PK in this subject population if data is collected from  $\geq 40\%$  of the subjects. Subjects' current weight will be used as one of the primary covariates for CL/F and V/F in the model to characterize body weight mediated changes in CL/F within a subject. Relationship between various measures of systemic exposure of tofacitinib (e.g., observed or model predicted trough or 2-hour post-dose concentrations) and efficacy/long-term safety outcomes may be explored using appropriate methodology. Details will be captured in a separate Population Modeling Analysis Plan (PMAP).

### 6.4. Subset Analyses

Efficacy and safety analyses in sJIA1 analysis subset, sJIA2 analysis set, pJIA analysis subset, ERA analysis subset and PsA analysis subset are discussed in Sections [6.1](#) and [6.2](#).

### 6.5. Baseline and Other Summaries and Analyses

Baseline disease characteristics are listed in Section [3.4.2](#).

For variables defined specifically in subjects with ERA and PsA, ERA analysis sets and PsA analysis set will be used for baseline summaries, respectively.

For variables that are defined in all subjects, baseline summaries will be provided for FAS, and also for sJIA1 analysis set, sJIA2 analysis set, pJIA analysis set, ERA analysis set and PsA analysis set.

## 6.6. Safety Summaries and Analyses

Please see Section 6.1 for descriptive summaries of safety endpoints.

In addition, the Incidence Rates (IRs) of adverse events specified in the table below will be calculated.

Treatment emergent adverse events (TEAEs)
Serious adverse events (SAEs)
Adverse events (AEs) leading to discontinuation from study
All-cause deaths
All infections
Serious infections (SIs)
All herpes zoster (HZ, from the clinical database and adjudicated a events)
Adjudicated tuberculosis (TB) a
Adjudicated opportunistic infections (OIs) a
Adjudicated OIs excluding TB a
Adjudicated OIs excluding TB and HZ a
Hematologic events (anaemia, neutropenia, lymphopenia, and thrombocytopenia, respectively)
Adjudicated malignancy excluding non-melanoma skin cancer (NMSC) a
Adjudicated NMSC a
Adjudicated lymphoma a
Adjudicated major adverse cardiovascular events (MACE) a,b
Adjudicated deep vein thrombosis (DVT) a
Adjudicated pulmonary embolism (PE) a
Adjudicated venous thromboembolism (VTE) (i.e., adjudicated DVT or adjudicated PE) a
Arterial thromboembolism (ATE, from the clinical database and the adjudicated a events)
Thromboembolism (TE) (i.e., adjudicated DVT a , adjudicated PE a , or ATE)
Adjudicated drug-induced liver injury (DILI) a and other hepatic events c
Renal events d
Adjudicated gastrointestinal perforations a
Adjudicated interstitial lung disease (ILD) e
Adjudicated macrophage activation syndrome (MAS) a , applicable to subjects with sJIA only.

Abbreviations: AE = adverse event; ATE = arterial thromboembolism; DILI = drug-induced liver injury; DVT = deep vein thrombosis; GI = gastrointestinal; HZ = herpes zoster; ILD = interstitial lung disease; MACE = major adverse cardiovascular events; MAS = macrophage activation syndrome; MedDRA = Medical Dictionary for Regulatory Activities; NMSC = non-melanoma skin cancer; OI = opportunistic infection; PE = pulmonary embolism; SAE = serious adverse event; SI = serious infection; SMQ = Standardised MedDRA Queries; TEAE = treatment emergent adverse event; TB = tuberculosis; TE = thromboembolism; VTE = venous thromboembolism.

- Adjudicated by Adjudication Committees independent and external to Pfizer.
- Components: cardiovascular death, non-fatal myocardial infarction, and non-fatal stroke.
- Including SMQs: Hepatic failure, fibrosis, and cirrhosis, and other liver damage-related conditions; and Hepatitis, non-infectious.
- Including Acute renal failure SMQ.
- Adjudicated by an internal review committee.

Incidence Rates (IRs) will be calculated and presented in 100 subject-years and defined as follows:

$$\text{IR} = 100 * \frac{\text{Number of Unique Subjects with Event during the Risk Period (RP)}}{\text{Sum of Event Exposures for all Subjects (Subject-Years of Exposure)}}$$

The numerator of the IR will include subjects counted only once as soon as they experience a first event during their individual risk period (RP) defined below.

The denominator will be the sum of the times to event for those who experience an event during the risk period and the lengths of risk periods for those who do not experience an event. If a subject experiences multiple instances of the same event, the time to first occurrence of the event will be considered.

In general, a subject is considered at risk to experience an AE while on tofacitinib treatment and within 28 days of stopping tofacitinib treatment. Thus, the risk period extends from the subject's first dose of tofacitinib up to the date of last dose of tofacitinib + 28 days.

For the final analysis, the RP is defined as:

$$\text{RP} = \min(\text{last dose date} + 28 \text{ days}, \text{last contact date}) - \text{first dose date} + 1 \text{ day}.$$

The last contact date will be the maximum of (AE start date, AE stop date, last study visit date, withdrawal date). If a subject is dead, the last contact date will be the death date.

For an interim analysis with a data cutoff date, the RP is defined as:

$$\text{RP} = \min(\text{last dose date} + 28 \text{ days}, \text{last contact date}, \text{data cutoff date}) - \text{first dose date} + 1 \text{ day}.$$

95% CI (corresponding to  $\alpha=0.05$ ) for this IR will be calculated based on the assumption that the actual count of cases (i.e., unique subjects with events) arises from an exact Poisson distribution. The approach used in Daly (1992) describing the calculation of exact confidence limits will be used. If  $x$  denotes the actual number of subjects with events, the (1

$-\alpha) \times 100\%$  confidence limit,  $x_L$  the lower confidence limit and  $x_U$  the upper confidence limit, then the following formula yields values for  $x_L$  and  $x_U$ ,

When  $x > 0$ ,

$$x_L = 0.5 * \chi^2(\alpha/2; 2x) \text{ and } x_U = 0.5 * \chi^2(1 - \alpha/2; 2x+2),$$

When  $x = 0$ ,

$$x_L = 0 \text{ and } x_U = 0.5 * \chi^2(1 - \alpha/2; 2x+2).$$

In the above notation,  $\chi^2(p; n)$  represents the  $p^{\text{th}}$  quantile of the chi-square distribution with  $n$  degrees of freedom. Once  $x_L$  and  $x_U$  are obtained, they are to be adjusted for the at-risk population per 100 subject-years by multiplying by 100.

In addition, all adjudicated events will be listed.

Additionally, Potential Hy's Law Cases, defined as patients with AST or ALT  $\geq 3$  x the upper limit of normal (ULN) concurrent with a total bilirubin  $\geq 2$  x ULN, will be summarized.

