7.2.5. Uveitis Exam

Uveitis exam must be performed by an ophthalmologist (or qualified equivalent per local practice) and will be done at Screening if no documented history of uveitis exam within past 6 months is available) then annually thereafter, and at the End of Study/Early Termination Visit if required

If there is documented history of uveitis exam within the past 6 months, the next exam will be done one year from the date of the previous exam, then annually thereafter, and at the End of Study/Early Termination Visit if required.

A uveitis exam at the End of Study/Early Termination Visit is not required if an exam has been performed within the past 6 months of the EOS/ET visit.

The window for this particular examination is ± 30 days relative to the visits where uveitis exam is to be performed. At all other visits the investigator should assess if there are potential changes in uveitis status and refer for formal evaluation if deemed clinically necessary. For JIA subtypes that may require more frequent uveitis examination, investigators should manage this type of examination according to local standard of care.

For subjects with sJIA, this exam is not required but if available, documentation of previous uveitis assessment(s) by an ophthalmologist (or qualified equivalent per local practice) should be reviewed, the date of the prior examination recorded, and the presence/absence of active uveitis documented. For subject with sJIA, the investigator should assess at all visits if there are potential changes in uveitis status and refer for formal evaluation if deemed clinically necessary.

Uveitis exam should be performed according to standard of care and the results (ie, a report) recorded in the source document. Development of new uveitis or worsening of existing uveitis according to Standardization of Uveitis Nomenclature (SUN) criteria should be reported as adverse events in the CRF.

The activity of the anterior chamber (AC) inflammation will be evaluated according to the SUN criteria, where the activity of AC inflammation is graded from 0 to 4 (grade/cells in field: 0/<1, 0.5+/1–5, 1+/6–15, 2+/16–25, 3+/26–50, 4+/>50) (Jabs 2005).¹²

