9.3. Safety Analysis

All the safety data, including the following, will be summarized descriptively through appropriate data tabulations, descriptive statistics, and graphical presentations:

- Adverse events will be summarized according to Pfizer standards.
- Safety laboratory tests will be summarized according to Pfizer standards.
- Special attention will be given to the following safety criteria: neutrophil counts, lymphocyte counts, serum creatinine levels, liver tests, hyperlipidemia, diabetes, anemia and hypertension.
- Serious infections, defined as any infection (viral, bacterial, and fungal) requiring hospitalization or parenteral antimicrobials or meets other criteria that require it to be classified as a serious adverse event, will be summarized.
- Special attention will be given to the following safety endpoints: MAS, uveitis, cytopenias, malignancies, cardiovascular diseases, gastrointestinal perforations and validated assessments of growth and pubertal development.

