## 6. ANALYSES AND SUMMARIES

### 6.1. Primary Endpoints

The primary endpoints are standard laboratory safety data, adverse event (AE) reports, body weight, height and tanner stages. The Safety Analysis Set (SAS) will be used for analysis. For some endpoints, e.g., overall AE summary and AEs by SOC and PT, analyses will also be performed in sJIA2 analysis set and any additional summaries will be detailed in the programming plan.

All the safety data, including the following, will be summarized descriptively through appropriate data tabulations, descriptive statistics, and graphical presentations by visit:

- Adverse events will be summarized according to Pfizer standards.
- Safety laboratory tests will be summarized according to Pfizer standards.
- Subjects meeting certain cutoffs will be summarized for the following parameters: neutrophil counts, lymphocyte counts, serum creatinine levels, liver tests, lipid levels, hemoglobin.
- Subjects meeting discontinuation and monitoring criteria (see Protocol Appendix 8) will be summarized.
- Serious infections will be summarized.
- Incidence rate will be calculated for AEs of special interest. See Section [6.6](#) for details.
- For pubertal development as measured by Tanner Stage, a shift table of Tanner Stages from baseline to each post-baseline visit will be constructed by age group (2 to <6 years, 6 to <12 years, and 12 years or older) for males and females separately. The percentages in the shift table will be based on the number of subjects with available tanner stage data at both baseline and the post-baseline visit of interest.

- For assessment of growth as measured by body weight and height, a table of descriptive statistics for body weight and height standardized Z-scores (actual values and changes from baseline) at each visit will be constructed by age group (2 to <6 years, 6 to <12 years, and 12 years or older) for males and females separately.

Height (weight) Z-score is calculated using the following formulation:

$$Z = \frac{(X/M)^L - 1}{LS}, L \neq 0$$

Or

$$Z = \ln(X/M) / S, L = 0$$

where X is the physical measurement (e.g., height, weight) and L, M, and S are the values from standardized growth charts provided by the US Centers for Disease Control website (<http://www.cdc.gov/GrowthCharts/>) by gender for children from birth to 240 months. The Z-score cannot be calculated if age >240 months.

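### Uveitis is a special-attention safety endpoint in Protocol 9.3, but the SAP specifies no uveitis safety summary and its list of incidence rates has no uveitis row

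*SAP*

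**What the plan says.** Protocol 9.3 states: "Special attention will be given to the following safety endpoints: MAS, uveitis, cytopenias, malignancies, cardiovascular diseases". The list goes on to gastrointestinal perforations and to growth and pubertal development, seven items in all.

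Protocol 7.2.5 sets up the data collection. Children without sJIA have an eye exam by a specialist each year, and some subtypes are examined more often under local care. The section then says: "Development of new uveitis or worsening of existing uveitis according to Standardization of Uveitis Nomenclature (SUN) criteria should be reported as adverse events". Two limits are written in. On sJIA: "For subjects with sJIA, this exam is not required but if available". On the final visit, the exam "is not required if an exam has been performed within the past 6 months of the EOS/ET visit".

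In the SAP, section 6.1 says "Incidence rate will be calculated for AEs of special interest" and points to section 6.6. Section 6.6 restricts the rates to a table: "the Incidence Rates (IRs) of adverse events specified in the table below will be calculated". Section 6.1 also relies on routine adverse-event tables, giving as examples "overall AE summary and AEs by SOC and PT". The only analysis text in the SAP that uses uveitis is Appendix 1.5, where it is one component of clinical inactive disease, an efficacy endpoint.

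**The concern.** Long-term safety is the primary objective, and the protocol picks out uveitis by name. It also asks children without sJIA to have repeated eye exams, and it sends the findings into the adverse-event database. The SAP then specifies nothing that says how many children developed uveitis or got worse, or at what rate.

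The rate method in SAP 6.6 would supply both: "The numerator of the IR will include subjects counted only once as soon as they experience a first event", and the count is divided by time at risk. A preferred-term row counts a child once within its own term, but one child can appear in several rows. If uveitis events are coded to more than one term, the number of affected children cannot be read off the table. Time in study also varies between subjects (SAP 2.2), so a crude percentage for uveitis cannot be set beside the exposure-adjusted rates for the other named events. Fixing the term grouping in advance also prevents a choice of terms after the data are seen.

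**Working it through.** **Step 1: set the two lists side by side.** The documents give no uveitis rate, count or precision target, so there is no figure to reproduce. The check is one of coverage.

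| Protocol 9.3 item | Safety summary specified in the SAP |
|---|---|
| MAS | 6.6, adjudicated row (sJIA only) |
| Uveitis | None |
| Cytopenias | 6.6, hematologic events, by type |
| Malignancies | 6.6, three adjudicated rows |
| Cardiovascular disease | 6.6, adjudicated MACE |
| GI perforations | 6.6, adjudicated row |
| Growth and puberty | 6.1, Z-score tables and Tanner shift tables |

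The SAP 6.6 table has 26 rows, and none is uveitis. One of the seven items has no dedicated summary.

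**Step 2: look for another route in the SAP.** The SAP 6.6 listing covers adjudicated events, but Protocol 9.7 names no uveitis committee. SAP 6.1 leaves additional summaries to a programming plan; that clause sits in the sentence on the sJIA2 set and does not mention uveitis. What remains is the SOC and preferred-term table. A SOC total would mix uveitis with other eye events.

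**Step 3: overlap between preferred-term rows (illustration).** Suppose three uveitis terms show 3, 2 and 2 children. With full overlap there are 3 affected children; with none there are 3 + 2 + 2 = 7. At an assumed 680 subject-years:

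- 100 × 3 / 680 = 0.44 per 100 subject-years
- 100 × 7 / 680 = 1.03 per 100 subject-years

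**Step 4: crude percentage against rate (illustration).** Take the projected 340 subjects (Protocol 9.1) and assume x = 5 affected children. The crude figure is 5/340 = 1.5%. Rate = 100 × x / PY. Following SAP 6.6, the 95% limits on the count are xL = 0.5 × χ²(0.025; 2x) and xU = 0.5 × χ²(0.975; 2x + 2), scaled by 100/PY. Total exposure is used as an approximation to time at risk.

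| Assumed mean follow-up | PY | Rate per 100 PY (95% CI) |
|---|---|---|
| 1 year | 340 | 1.47 (0.48 to 3.43) |
| 2 years | 680 | 0.74 (0.24 to 1.72) |
| 4 years | 1360 | 0.37 (0.12 to 0.86) |

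The crude percentage is the same in each row, while the rate changes fourfold. With no cases, the upper limits would be 1.08, 0.54 and 0.27.

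**Step 5: how far the exam schedule could move the rate (illustration).**

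- *No required exam in sJIA.* The number of subjects without sJIA is not given. The amendment history (Protocol Appendix 17, Amendment 7) puts the projected total at about 290 before A3921165 subjects were added. That figure is used here only for scale, and it still contains sJIA subjects from A3921104. If all 5 cases lie in that group and mean exposure is equal, the rate rises by a factor of 340/290 = 1.17.
- *Annual exams.* If each case is found 6 months late, the denominator gains 5 × 0.5 = 2.5 PY. That is 2.5/340 = 0.7% at the shortest follow-up and 2.5/1360 = 0.2% at the longest. Coarse onset times hardly matter. Cases never examined matter more.

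**The case against.** The strongest reply is that nothing promised has been withheld. Protocol 9.3 asks for special attention and descriptive summaries, not a rate, and the SAP never labels uveitis an adverse event of special interest. Protocol 2.3.1 does not list uveitis among the findings that may be associated with tofacitinib, and both documents use it in defining inactive disease. Routine tables are then a defensible choice, and the database would allow a count and rate later. This stands as far as it goes: no protocol commitment is broken. It does not explain why uveitis alone on that list gets no summary, and the SAP gives no reason. MAS is also a complication of the disease, yet it has a row.

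A reader might infer that uveitis goes unreported, or that no summary is planned anywhere. The documents do not support either reading. The events appear by preferred term and in the aggregate adverse-event rates, and the sponsor standards and programming plan, which were not available, could contain more. The claim is only that the SAP specifies none.

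Three narrower objections are fair:

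- The count of one in seven covers the second special-attention list in Protocol 9.3. The first list includes diabetes and hypertension, which have no row in SAP 6.6 either and are not among the SAP 6.1 cutoffs.
- No document shows that uveitis events would spread over several preferred terms.
- A single row for new and worsening uveitis mixes two at-risk groups, because only a child who already has uveitis can worsen. The fix should separate them.

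**Conclusion.** The gap is real and limited. The SAP followed as written gives crude preferred-term counts for uveitis, while the other six items on the protocol's list have a rate row or tables of their own. It would be wrong to infer that any safety estimate is biased, that data are lost, or that the protocol is contradicted. The study is descriptive, and no test or decision rule depends on this.

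The size of the defect is one missing summary among seven named items. The rates above show what a crude percentage hides under variable follow-up; their event counts and exposures are assumptions and do not estimate what this trial will find. The conclusion rests on the SAP text alone. If the sponsor's standards or the programming plan already define a uveitis grouping and a rate, a cross-reference in the SAP is enough. This is a cheap improvement.

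**What to change.** Add one row to the SAP 6.6 table: uveitis, new or worsening, reported as an adverse event, not adjudicated. Define it by a MedDRA grouping fixed before database release. The renal row is the precedent: it is unadjudicated and uses an SMQ. Count unique subjects and use the existing rate and exact Poisson limits.

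Show the row overall and for subjects without sJIA, who have the required annual exam. Also show new-onset and worsening events separately. Separate denominators would need uveitis status at entry, which SAP 3.4.2 does not list among its baseline summaries; where that status is unclear, give counts only.

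Footnote that exams are annual, or more frequent under local care; that they are not required in sJIA; and that the final exam may be omitted if one was done in the past 6 months, so late silent cases can be missed.

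The cost is one term grouping, a few table rows and a sentence or two of SAP text. No new assessment is needed. The drawback is that the rate will partly reflect how often children are examined, which the footnote makes plain.
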